prolonged inflammation, and an increased risk of infection. Conventional treatment strategies may not adequately address these challenges, necessitating the exploration of novel regenerative approaches.

Platelet-derived growth factors, particularly Advanced Platelet-Rich Fibrin (A-PRF), have recently gained attention as potential promoters of wound healing and tissue regeneration. A-PRF is a biologically active autologous scaffold that aligns with the physiological principles of wound healing by providing a sustained release of key growth factors such as platelet-derived growth factor (PDGF), transforming growth factor- β (TGF- β), and vascular endothelial growth factor (VEGF). These growth factors are essential for cellular migration, angiogenesis, and extracellular matrix remodeling.

In diabetic patients, chronic hyperglycemia, prolonged inflammation, microvascular dysfunction, and impaired collagen synthesis contribute to delayed wound healing. The theoretical premise of A-PRF is that it may enhance the natural healing cascade in diabetic individuals by compensating for impaired biological responses. However, despite promising biological rationale and preliminary clinical evidence, there remains limited high-quality clinical data evaluating the effectiveness of A-PRF in post-extraction socket healing in diabetic patients.

Therefore, this study will aim to evaluate the effectiveness of A-PRF in enhancing soft tissue healing and reducing post-extraction complications in diabetic individuals using a split-mouth randomized clinical trial design. The findings are expected to contribute to evidence-based clinical protocols and improve standards of care for diabetic patients undergoing dental extractions at King Abdulaziz University Dental Hospital.

Research Question

Does the application of growth factors derived from platelets accelerate healing and reduce post-extraction complications in diabetic individuals?

Research Hypotheses

Null Hypothesis (H0):

The application of platelet-derived growth factors will not enhance healing or reduce post-extraction complications in diabetic individuals.

Alternative Hypothesis (H1):

The application of platelet-derived growth factors will accelerate healing and reduce post-extraction complications in diabetic individuals.

Objectives

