This double-blinded, randomized controlled clinical trial will be conducted at King Abdulaziz University Dental Hospital. Ethical approval has been obtained from the Institutional Review Board, and the study will be conducted in accordance with the Declaration of Helsinki (2013). Written informed consent will be obtained from all participants prior to enrollment.

Sample and Study Population

The sample size has been calculated using G*Power software with an alpha level of 0.05, 80% power, and a medium effect size of 0.5. Diabetic patients aged 18 years or older requiring bilateral extraction of the same tooth type will be recruited. Patients with systemic conditions other than diabetes, bleeding disorders, pregnancy, lactation, or tobacco use will be excluded.

A split-mouth design will be employed, with one extraction site randomly assigned to receive A-PRF and the contralateral site serving as a control. Randomization will be performed using a computer-generated sequence. Patients and outcome assessors will remain blinded throughout the study.

Clinical Procedure

All extractions will be performed using a standardized atraumatic technique by a single calibrated operator. After extraction, venous blood will be collected to prepare A-PRF using a low-speed centrifugation protocol. The A-PRF membrane will be placed into the assigned socket, while control sockets will receive no adjunctive material. All sites will be sutured using standardized suture material.

Outcome Measures

Healing will be assessed quantitatively using digital intraoral scanning at baseline, 1 week, and 3 weeks post-extraction. Patient-reported outcomes, including pain, swelling, and satisfaction, will be collected using validated questionnaires at specified follow-up intervals.

Statistical Analysis

Data will be analyzed using Stata software (Version 16). Normality will be assessed using the Shapiro–Wilk test. Paired statistical tests will be used to compare healing outcomes between A-PRF-treated and control sites, with significance set at $p < 0.05$.

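### A-PRF is randomised to one side of the mouth, but the plan states no left-right balance and no side term: the paired test stays valid but may lose precision

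*Combined protocol and SAP*

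**What the plan says.** All of this is in Materials and Methods of the combined protocol and SAP.

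- **Design (Sample and Study Population).** Each patient contributes two sites, "with one extraction site randomly assigned to receive A-PRF and the contralateral site serving as a control". What chance decides is therefore whether the left or the right socket is treated.
- **Allocation (same section).** "Randomization will be performed using a computer-generated sequence". Blocking and left-right balance are not mentioned.
- **Operator (Clinical Procedure).** "All extractions will be performed using a standardized atraumatic technique by a single calibrated operator". The operator's handedness and the order in which the two sides are treated are not given.
- **Analysis (Statistical Analysis).** "Paired statistical tests will be used to compare healing outcomes between A-PRF-treated and control sites", after a Shapiro–Wilk check. Side does not appear.
- **Power statement (same section as the design).** It reads: "The sample size has been calculated using G*Power software with an alpha level of 0.05, 80% power, and a medium effect size of 0.5". No number of patients, test, sidedness or SD is stated, nor what the 0.5 is standardised on.

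**The concern.** Pairing removes differences between patients. It does not remove a systematic difference between left and right. Suppose left sockets heal better than right by a constant amount. A patient with A-PRF on the left then shows the treatment effect plus that amount, and a patient with A-PRF on the right shows the effect minus it. Across patients this alternation looks like random error and inflates the SD of the paired difference.

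The layout is that of a two-period crossover with side in the place of period, and period is routinely put in the model there. If one operator does have an access or working-order effect, it could run the same way in every patient, because there are no other operators to average over.

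Precision is what is at stake. Side will be known for every patient, so a plain paired test would leave unused information that the design already provides.

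**Working it through.** **Inputs from the plan.** Alpha 0.05, power 80%, effect size 0.5. The alternative in Research Hypotheses is worded directionally, but no sidedness is given for the test.

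**Assumptions.** A two-sided paired t-test, and a left-right gap s, whose size the documents do not give.

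**Step 1, implied sample size.** The plan states no number, so there is nothing to reproduce. The noncentral t with standardised paired effect 0.5 gives 34 pairs two-sided (power 80.8%) or 27 one-sided (81.2%). I use 34.

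**Step 2, model.** For patient i let D = A-PRF minus control:

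D_i = τ + s·z_i + e_i, with z_i = +1 if A-PRF is on the left and −1 if on the right, and e_i with SD 1.

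Here s is the full left minus right difference and τ = 0.5. Both are in SDs of the difference after side is removed.

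**Step 3, effect on the error.** Without a side term the SD of D is √(1 + s²):

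- s = 0.25: √1.0625 = 1.031, an interval about 3% wider; effective effect size 0.5/1.031 = 0.485.
- s = 0.5: √1.25 = 1.118, about 12% wider; effective effect size 0.5/1.118 = 0.447.

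**Step 4, power at 34 pairs with 17 on each side.** Unadjusted: the mean of D has variance 1/34, while its estimated variance uses a sum of squares distributed as χ²(32) plus a noncentral χ²(1) with noncentrality 34s², divided by 33. Adjusted: D is regressed on z, and the intercept is tested on 32 degrees of freedom.

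| s | Unadjusted | Adjusted |
|---|---|---|
| 0 | 80.8% | 80.7% |
| 0.25 | about 79% | 80.7% |
| 0.5 | about 73% | 80.7% |

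The gain from adjusting is about 2 points at 0.25 and about 7 at 0.5. The cost at s = 0 is 80.8 − 80.7 = 0.1 point.

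**Step 5, the same with a simple (unblocked) list.** Unadjusted power is 78.4% at s = 0.25 and 71.6% at s = 0.5. Adjusted power is about 79.5% throughout, because chance imbalance makes the intercept less precise. The cost at s = 0 is 80.8 − 79.5 = 1.3 points. The chance of a 22:12 or worse split is 2·P(X ≥ 22) = 12.1% for X binomial(34, 0.5).

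**Step 6, type I error.** With a simple list the unadjusted test stays at about 5% for every s tried. With a balanced list it falls to 4.1% at s = 0.3 and about 3% at s = 0.5. The adjusted test stays at about 5%. Balancing side without adjusting for it therefore makes the test conservative.

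**Step 7, the other reading of 0.5.** If 0.5 is standardised on the SD of the observed difference, side variation is already in that SD. The noncentral-t formula then gives 80.8% unadjusted whatever s is. The effect in residual SDs becomes 0.5·√(1 + s²). At s = 0.5 that is 0.559, and adjusted power is 88.5%.

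**The case against.** A reader might infer that the stated 80% power is not kept. The documents do not support that, for three reasons. No sample size is given, so there is no achieved power to check. The power statement says only "a medium effect size of 0.5"; for a paired test this is usually standardised on the observed difference, and under that reading 80% is kept (step 7). And no left-right gap is reported or sized anywhere.

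A reader might also infer that a single operator implies a side effect. It does not. The plan describes a calibrated operator, a standardised technique and suture material, and the same type of tooth on both sides, all of which argue for a small gap. One operator means only that a gap, if present, could be consistent across patients.

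Nor may a reader infer bias. Randomising the side protects the paired comparison, and an uneven split under a simple list is ordinary chance imbalance that the test already allows for.

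The scale of the illustration deserves the same caution. A gap of 0.5 equals the whole planned effect. At gaps of 0.2 to 0.3 the loss is only about 1 to 3 points, and at 0.1 it is under 1 point. With a simple list, a side term gains only about 1 point at 0.25 and costs 1.3 at zero.

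All of this stands. A plain paired test is an acceptable split-mouth analysis, and the missing sample size and undefined effect size are the larger gaps in this section. What survives is narrower: with balanced sides, adjustment costs almost nothing if there is no gap and gains precision if there is one, under either reading of 0.5.

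**Conclusion.** The point holds as a possible loss of precision and not as an error in the test. The plan randomises side, states no balance on it and leaves it out of the analysis. Any systematic left-right difference would therefore widen the interval for the A-PRF effect, and with a side-balanced list it would also make the plain paired test conservative.

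The size is unknown. It is about 2 points of power for a gap of 0.25 residual SDs and about 7 points for a gap of 0.5. These figures rest on 34 pairs, a two-sided test, normal errors, balanced sides, and 0.5 defined after side is removed. If 0.5 refers to the observed difference, nothing is lost against the stated 80%, and adjustment only adds power. This is a cheap improvement worth making, of lower priority than stating the sample size and defining the effect size.

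**What to change.** The cover letter says that nobody had been enrolled at registration. If that is still so, both changes can be made in advance.

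1. **Allocation.** Generate the side list in permuted blocks of varying size, so that A-PRF falls on each side in about half the patients.
2. **Analysis.** Pre-specify a linear regression of the within-patient difference (A-PRF minus control) on side coded −1/+1. Report the intercept as the A-PRF effect with its 95% CI.

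Make the two changes together: balance alone leaves the plain test conservative if a gap exists, and a side term alone carries the larger cost shown in step 5. Because a normality check is planned, also name the procedure for non-normal differences. One option is a permutation test of the same intercept that re-draws side within the blocks. State the number of patients and what the 0.5 is standardised on, so that the effect on power can be judged.

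The cost is a few sentences and one degree of freedom. If there is no side effect, that is about 0.1 point of power with balanced sides (about 1.3 points with a simple list). No extra patients, visits or data are needed. Adding side after the results are known would be post hoc.
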